11.2.2. Beck Depression Inventory (BDI-II)

The Beck Depression Inventory (BDI-II) is a 21-item measure of the severity of current depressive symptoms, extensively validated for use in both medical and mental health populations. While this instrument does not provide a psychiatric diagnosis of depression and has considerable overlap with PTSD associated symptoms ([Resick et al, 2017](#)), it does provide a continuous scale for measuring changes in the severity of symptomatology.

The patient will be asked to complete this questionnaire at all in-clinic study visits. At Visit 1 and Visit 2, patients whose responses are indicative of suicidal ideation, as defined by a response to Item #9 of ≥ 1 should be carefully evaluated and compared to the patient's C-SSRS responses, and appropriate intervention prescribed, if indicated. In addition, patients' BDI-II responses at Screening and Baseline (Visits 1 and 2) should be reviewed by the investigator as part of the comprehensive evaluation of the patient's psychiatric status and overall eligibility, since patients suffering from severe depression should be screen failed and referred for appropriate psychological evaluation or care, as necessary. After Visit 1, the responses to Item #9 should be monitored along with C-SSRS responses to ensure that there is no increase in suicidal ideation during the study, and the total score should also be monitored to ensure the patient's psychological status remains stable.

11.2.3. Clinical Global Impression of Improvement (CGI-I)

The CGI-I will be completed by an Investigator to evaluate the patient's status since initiation of treatment. The CGI-I, status since initiation of treatment, is the first key secondary efficacy endpoint in this study. The CGI-I should be completed toward the end of each in-clinic post-Baseline study visit once all of the assessments are available for the investigator's review.

11.2.3.1. CGI-I Assessments at Weeks 4, 8, and 12

Once the patient has been randomized, an Investigator will complete the CGI-I assessment after 4, 8, and 12 weeks of treatment (Visits 4 -6) in order to assess the overall change in the patient's status since Baseline and answer the following question:

Since the initiation of treatment at Visit 2, the patient is:

- 1 = Very much improved
- 2 = Much improved
- 3 = Minimally improved
- 4 = No change
- 5 = Minimally worse
- 6 = Much worse
- 7 = Very much worse

11.2.4. Patient Global Impression of Change (PGIC)

The PGIC is a validated, self-report instrument to gauge the patient's assessment of change in condition. This form will be completed by the patient after 4, 8 and 12 weeks of treatment (Visits 4, 5 and 6, respectively). The patient will answer a single question:

Since the initiation of study medication, overall, my PTSD symptoms are:

- 1 = Very much improved
- 2 = Much improved
- 3 = Minimally improved
- 4 = No change
- 5 = Minimally worse
- 6 = Much worse
- 7 = Very much worse

11.2.5. PROMIS Sleep (short form) Scale

PROMIS refers to the Patient-Reported Outcome Measurement Information System (www.nihpromis.org), an NIH-funded initiative to develop instruments to be used across chronic conditions.

The PROMIS Sleep scale (short form 8a) will be assessed at Baseline (Visit 2) and after 4, 8, and 12 weeks of treatment (Visits 4, 5, and 6, respectively).

11.2.6. Sheehan Disability Scale (SDS)

The SDS scale is a self-report questionnaire that was designed to assess the patient's view of the degree to which symptoms have disrupted work, social life/ leisure activities, and family life/ home responsibilities during the past 1 week ([Sheehan & Sheehan, 2008](#)). In addition, the SDS asks the patient to provide the number of days or work lost as well as unproductive days in the past week. The SDS scale will be completed by the patient at Baseline (Visit 2), and after 4, 8, and 12 weeks of treatment (Visits 4, 5, and 6, respectively).

11.3. Safety Parameters

Safety will be assessed by evaluation of adverse events, responses on the C-SSRS and BDI-II, clinical laboratory tests, vital signs, weight, patient ratings of sexual function assessed by the CSFQ-14, and patient-rated assessments of morning sedation as assessed by the MTRSS.

11.3.1. Adverse Events (AEs)

Patients will be monitored for AEs throughout the study from the time that the patient signs an informed consent and onward. AEs that are spontaneously reported, elicited or observed are to be recorded on the CRF with the date, time of onset, date and time of resolution, severity, seriousness, causality (relationship to study medication), actions required, and outcome.

To elicit AEs, non-leading, simple questions with minimal connotations should be used as the initial questions at all evaluation points during the study. Examples of these questions can be:

- How have you felt since your last visit?
- Have you had any health problems since your last visit?

If an AE occurs, the investigator will institute support and/or treatment as deemed appropriate. If a non-serious AE is unresolved on the last day of the study, an effort should be made to follow up until the AE is resolved or stabilized, the patient is lost to follow-up, or there is some other resolution of the event.

There are many symptoms associated with PTSD that can vary in intensity and frequency over time. Only symptoms that significantly worsen or become more frequent, in the opinion of the patient and outside of their normal experience, should be reported as an adverse event.

If a patient reports an oral cavity adverse event, the Investigator should examine the oral cavity to confirm the presence or absence of any irritation or other signs. Additional details related to onset, duration, severity and reversibility of the oral cavity event will be documented ([Section 11.3.5](#)).

Additional information regarding definition and reporting requirements for adverse events, serious adverse events, and pregnancies is provided in [Section 11.3.1](#).

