12. DEFINITIONS, RECORDING, AND REPORTING OF ADVERSE EVENTS

12.1. Definition of Adverse Events

According to International Conference on Harmonization (ICH) guidance E2A, Clinical Safety Data Management: Definitions and Standards for Expedited Reporting, an adverse event (AE) is

any untoward medical occurrence in a patient or clinical investigation patient administered a pharmaceutical product and which is not necessarily required to have a causal relationship with this treatment. An AE can therefore be any unfavorable and unintended sign (including an abnormal laboratory finding, for example), symptom, or disease temporally associated with the use of a medicinal product, whether or not considered related to the medicinal product.

A treatment-emergent AE (TEAE) is an AE that either commenced following initiation of study treatment or was present prior to study treatment but increased in frequency or severity following initiation of study treatment.

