The following adverse reactions have been reported in postmarketing experience (AMRIX or cyclobenzaprine IR), in clinical studies of cyclobenzaprine IR (incidence <1%), or in postmarketing experience with other tricyclic drugs:

Body as a Whole: Syncope; malaise; chest pain; edema.

Cardiovascular: Tachycardia; arrhythmia; vasodilatation; palpitation; hypotension; hypertension; myocardial infarction; heart block; stroke.

Digestive: Vomiting; anorexia; diarrhea; gastrointestinal pain; gastritis; thirst; flatulence; edema of the tongue; abnormal liver function and rare reports of hepatitis, jaundice, and cholestasis; paralytic ileus, tongue discoloration; stomatitis; parotid swelling.

Endocrine: Inappropriate ADH syndrome.

Hematologic and Lymphatic: Purpura; bone marrow depression; leukopenia; eosinophilia; thrombocytopenia.

Hypersensitivity: Anaphylaxis; angioedema; pruritus; facial edema; urticaria; rash.

Metabolic, Nutritional and Immune: Elevation and lowering of blood sugar levels; weight gain or loss.

Musculoskeletal: Local weakness; myalgia.

Nervous System and Psychiatric: Seizures, ataxia; vertigo; dysarthria; tremors; hypertonia; convulsions; muscle twitching; disorientation; insomnia; depressed mood; abnormal sensations; anxiety; agitation; psychosis, abnormal thinking and dreaming; hallucinations; excitement; paresthesia; diplopia; serotonin syndrome; neuroleptic malignant syndrome; decreased or increased libido; abnormal gait; delusions; aggressive behavior; paranoia; peripheral neuropathy; Bell's palsy; alteration in EEG patterns; extrapyramidal symptoms.

Respiratory: Dyspnea.

Skin: Sweating; photosensitization; alopecia.

Special Senses: Ageusia; tinnitus.

Urogenital: Urinary frequency and/or retention; impaired urination; dilatation of urinary tract; impotence; testicular swelling; gynecomastia; breast enlargement; galactorrhea.

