### **10.1 Adverse Events**

All AEs, treatment-emergent adverse events (TEAEs), and SAEs will be coded using MedDRA, version 19.0.

TEAEs are defined as either new onset AEs with an onset at the time of or following the start of treatment through ten days after the last dose of study medication, or a recurrence of an AE (or medical history) present prior to randomization but increasing in severity, frequency or relationship at the time of or following the start of treatment

An AE summary table will be presented for the following:

- TEAEs by severity
- TEAEs leading to study drug discontinuation
- TEAEs by relationship
- SAEs

Summaries of incidence rates (frequencies and percentages) of individual AEs by MedDRA SOC and preferred term will be prepared. Such summaries will be displayed for all TEAEs, TEAEs by maximum severity, and TEAEs by strongest relationship to study drug.

Each participant will be counted only once within each summation level (SOC; preferred term). If a participant experiences more than one TEAE within each summation level only, the TEAE with the strongest relationship or the maximum severity, as appropriate, will be included in the summaries of relationship and severity.

Adverse events of special interest pertaining to abuse potential (as defined in the January 2017 Assessment of Abuse Potential for Drugs – Guidance for Industry) will be analyzed separately by treatment group, SOC and preferred term, and displayed in tabular format.

In the AE data listings, all AEs will be displayed. AEs that are treatment-emergent will be flagged.

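### For non-serious worsening of PTSD-associated symptoms, Protocol 11.3.1 lets only the patient's opinion make it an adverse event, which conflicts with the protocol's and SAP's own AE and TEAE definitions

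*Protocol*

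**What the plan says.** Protocol 11.3.1 opens with a general rule: "AEs that are spontaneously reported, elicited or observed are to be recorded on the CRF". Later in the section it turns to the disease itself. It notes that "There are many symptoms associated with PTSD that can vary in intensity and frequency over time", and then restricts adverse event reporting for these symptoms: "Only symptoms that significantly worsen or become more frequent, in the opinion of the patient and outside of their normal experience, should be reported".

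Protocol 12.1 defines an adverse event as "any untoward medical occurrence in a patient or clinical investigation patient administered a pharmaceutical product". Its treatment-emergent definition includes an event that "was present prior to study treatment but increased in frequency or severity following initiation of study treatment". SAP 10.1 counts as treatment-emergent "a recurrence of an AE (or medical history) present prior to randomization but increasing in severity, frequency or relationship" from the start of treatment onward. Neither document makes the patient's view a condition of these definitions.

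Other rules also bear on psychiatric harm:
- Under Protocol 11.3.3, C-SSRS ideation of 4 or 5 is an SAE, and a post-baseline 2 or 3 is an AE if it is a significant change from baseline.
- Protocol 11.3.2 leaves the presence of ideation or behavior to the rater's judgment.
- Protocol 12.3 requires every SAE to be reported.
- BDI-II is monitored during the study (11.2.2) and analyzed as a safety measure (13.5; SAP 2.2.3).

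**The concern.** An investigator or rater often sees changes that a patient does not report as unusual, particularly in arousal, irritability or sleep. For PTSD-associated symptoms, the word *only* in 11.3.1 closes the observed route that the same section opened. A site that follows the sentence literally can omit an event that 12.1 and SAP 10.1 would count. Once it is off the CRF, analysis cannot put it back into the TEAE tables.

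The affected area is not remote from the drug. The cyclobenzaprine label in Protocol Appendix 3 lists, among other nervous system and psychiatric reactions, "insomnia; depressed mood; abnormal sensations; anxiety; agitation; psychosis, abnormal thinking and dreaming", and also aggressive behavior. Several of these overlap with the PTSD features named in Protocol Section 5: distressing dreams, insomnia, negative mood and heightened arousal. A drug effect that resembles the disease is plausibly the kind a patient is least likely to call abnormal for them. At stake is the completeness of part of the psychiatric rows in the AE tables.

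**Working it through.** The plan states no figure on this point and no arithmetic applies. The check compares the passages.

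**1. Scope of the restriction.** The sentence concerns symptoms associated with PTSD. A psychiatric event outside that group stays under the general rule and is recorded when observed.

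**2. Conditions imposed, by source.**
- *11.3.1, general rule:* reported, elicited or observed. Any of the three suffices.
- *11.3.1, PTSD symptoms:* worse (qualified by *significantly*) or more frequent, judged by the patient, and beyond that patient's normal experience. The adverb may attach only to *worsen*. The patient-opinion and normal-experience conditions appear to govern both limbs.
- *12.1, TEAE:* increased frequency or severity after treatment starts. No judge is named.
- *SAP 10.1, TEAE:* an earlier AE or medical history that increases in severity, frequency or relationship. No judge is named.

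**3. A case traced through the rules.** At Week 4 a clinician sees clearly greater agitation and poorer sleep than at baseline. The event is not serious, and the patient regards it as usual.
- General rule in 11.3.1: recorded, because observed.
- 12.1 and SAP 10.1: treatment-emergent, because severity rose.
- PTSD sentence in 11.3.1: not reported, because the patient does not endorse it.

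The rules give opposite answers for the same event, and nothing in the documents says which prevails.

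**4. What else would catch it.**
- The C-SSRS rules cover suicidal ideation and behavior. This case has neither.
- SAE reporting does not apply, because the event is not serious.
- BDI-II covers depressive symptoms. None of the other safety parameters in Protocol 11.3 is directed at agitation, aggression, nightmares or insomnia. MTRSS asks about morning grogginess.
- SAP 9.2.1 and 9.2.2 analyze CAPS-5 clusters and items, PROMIS sleep, CGI-I and PGIC by arm, so the information is not lost. It appears as efficacy data, in the form of mean changes and responder proportions. The SAP plans no safety table of CAPS-5 worsening. In SAP 9.1.3 both continuous responder graphs pool worsening with no improvement and with missing data, and the bar chart of change separates missing data but still pairs worsening with no improvement.
- Under Protocol 10.5.1, a patient who withdraws before day 11 has BDI-II and C-SSRS at the termination visit, but none of the four efficacy scales just named.

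**5. Size.** Sizing the loss would need the rate of non-serious PTSD-symptom worsening in each arm and the share that staff see but patients do not endorse. The documents give neither.

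**The case against.** The strongest reply is that a threshold is needed. PTSD symptoms fluctuate, and without one ordinary variation would fill the AE tables. The protocol uses significance thresholds elsewhere: 11.3.3 for C-SSRS scores of 2 or 3, and 11.3.8 for laboratory abnormalities. This stands. It supports keeping *significantly* and the normal-experience condition. It does not explain why the patient should be the sole judge, and 11.3.3 shows that the protocol can record psychiatric change without the patient's agreement.

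A reader might infer that psychiatric harms seen by staff go unrecorded in general. The documents do not support that. The sentence is confined to PTSD-associated symptoms, and suicidality, serious events and depressive symptoms each have a route without the patient-opinion test. Nor can the whole label list be treated as screened out. It includes psychosis, which is not shown to fall under the PTSD rule, and it pools postmarketing reports, immediate-release studies at under 1% incidence and other tricyclics.

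A reader might also express the loss as power. With assumed true rates of 10% and 4%, 275 per arm and two-sided 0.05, a normal approximation gives about 79%. If patients endorse 75%, 50% or 25% of events equally in both arms, it gives about 66%, 48% or 27%. This does not size the problem. The rates are invented, SAP 10.1 plans frequencies and percentages with no AE test, and equal endorsement leaves the relative risk at 10/4 = 2.5. On the same footing, a looser rule that added 10 or 20 points of background fluctuation to each arm (20% v 14%, 30% v 24%) would give about 47% or 36%.

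**Conclusion.** The inconsistency is real and narrow. For non-serious worsening of PTSD-associated symptoms, other than C-SSRS-defined ideation, 11.3.1 makes AE reporting turn solely on the patient's opinion. That contradicts the observed route in the same section and adds a condition that 12.1 and SAP 10.1 do not contain. Clinician-observed agitation, aggression, nightmares or insomnia that meets the TEAE definition can therefore be missing from the AE tables. The other safety rules reduce the gap without closing it, and the efficacy scales do not replace AE capture.

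No magnitude can be given. Nor can a direction of bias between arms be established, since nothing in the documents shows how endorsement would differ by treatment. The conclusion rests on sites applying the sentence literally; a site that gave priority to the general rule would record the event, and practice could then vary across about 45 sites. The primary efficacy analysis is not affected.

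**What to change.** In the PTSD-symptom sentence of Protocol 11.3.1, insert *or the investigator* after *patient*, so that either opinion is enough. Keep *significantly* and the normal-experience condition. They remain a threshold that the definitions in 12.1 and SAP 10.1 do not state, but they answer the fluctuation problem the section describes and fit the protocol's practice elsewhere.

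This changes a recording rule only; no visit, assessment or treatment rule is touched. The cost is one phrase, its inclusion in site training, and somewhat more psychiatric AEs in both arms. It acts only on events recorded after the change.

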11.3.2. Columbia-Suicide Severity Rating Scale (C-SSRS)

The C-SSRS is a questionnaire developed by researchers at Columbia University to assess suicide risk and to track suicidal ideation and behavior during clinical trials. This scale is intended to be used by individuals who have received training in its administration. The questions contained in the Columbia-Suicide Severity Rating Scale are suggested probes. Ultimately, the determination of the presence of suicidal ideation or behavior depends on the judgment of the individual administering the scale.

There are multiple versions of this questionnaire. At Visit 1, the “baseline/screening” questionnaire will be administered and the recall periods will be “lifetime” and “within the past 6 months” for suicidal ideation, and “within the past year” for suicidal behaviors. Patients whose responses are indicative of suicidal ideation with intent and/or plan (e.g., Type 4-5 ideation) within the past 6 months or a history of prior suicidal behavior within the past year will be excluded from participation, with recommended referral for appropriate intervention.

At all subsequent visits (Visit 2 through 6), the “since last visit” questionnaire will be administered, and the recall period on this will be “since the last visit”. Note that if there has been a significant change in responses indicative of increased suicide risk, appropriate intervention should be prescribed as described below.

11.3.3. Safety Planning Intervention (SPI)

The C-SSRS is completed at every visit in order to assess for changes in suicidality during the study. As a screening and baseline entrance criterion, patients exhibiting Type 4 or 5 ideation in the past 6 months or a history of suicidal behavior in the past 12 months are not eligible for the study due to this risk and should be referred for appropriate emergency care. If a patient scores a 4 or 5 at a clinic visit following randomization, the patient should be withdrawn from the study and referred for appropriate emergency care. If a patient scores a 4 or 5 at any clinic visit, it should be reported as a serious adverse event.

If a patient scores a 2 or 3 on the suicidal ideation section of the C-SSRS at any visit (including the Screening visit), the investigator and patient should work together to implement a Safety Planning Intervention (SPI). In addition, if a post-baseline score of 2 or 3 represents a significant change from the patient’s baseline status, it should be recorded as an adverse event. The recommended SPI for this study is the plan developed by [name] and [name] which has been adopted by the U.S. Veteran’s Administration (VA) ([Stanley & Brown, 2012](#)). The VA SPI is a brief clinical intervention aimed at mitigating suicide risk. It consists of a written, prioritized list of coping strategies and sources of support that patients can use to alleviate a suicidal crisis. Sites may use an internally-developed SPI if similar in scope and purpose to the VA SPI. Additional information and training on the implementation of an SPI will be provided prior to initiation of the study.

11.3.4. Physical Examination

A complete physical examination will be performed at Screening Visit 1 only. At a minimum, the physical examination will include the following components: HEENT (head, eyes, ears, nose, and throat), neck, chest and lungs, cardiovascular, abdomen, skin, and musculoskeletal. The physical examination may exclude rectal, genitourinary, and breast examinations.

11.3.5. Visual Examination of Oral Cavity

A visual examination of the oral cavity should be done at Screening (Visit 1), Baseline (Visit 2) and after 12 weeks (Visit 6) of treatment and/or at Early Termination. In addition to these regularly scheduled examinations, a visual inspection of the oral cavity (including the sublingual area) should be done any time a patient spontaneously reports an oral adverse event (other than transient sensory AEs such as tongue numbness, tingling or bitter taste) to confirm presence or absence of any irritation or other signs. Additional details related to onset, duration, severity and reversibility of oral events will be documented in the CRF.

11.3.6. Vital Signs, Height and Weight

Vital signs (sitting blood pressure and heart rate, respiratory rate, oral temperature, and weight) will be assessed at Screening (Visit 1), Baseline (Visit 2) and after 4, 8, and 12 weeks of treatment (Visits 4, 5, and 6/Early Termination). Height will be measured without shoes at Visit

1 only. The BMI will be a derived variable, based on height and weight entries. A BMI > 45 is an exclusion criterion.

